#### 5. Other measurements

### 5.1 Dietary intake

Data on dietary intake will be collected by a non-consecutive two day 24-hour dietary recall method (40). The recall will be interactive to allow for estimation of food quantities and sizes. The participants will be thoroughly probed to ensure that no foods consumed are forgotten. The time of food consumption will also be recorded. Participants will estimate their food portion sizes using a photographic atlas. The atlas utilizes photos of estimated food portions and their corresponding weight in grams.

#### 5.2 Physical activity

Physical activity will be measured using the validated short form of the international physical activity questionnaire (41).

### 6. Statistical analysis

This is a proof-of-concept (no power calculation). The study will use a pragmatic sample size. Intention to treat analysis will be conducted. Continuous variables will be presented as mean and standard deviation. Student t-test will be applied to compare means of endpoints between patient groups. Outcome variables will be checked for normality and transformed where necessary. To account for any missing data, analyses will be conducted using linear mixed models. Analysis will be performed using the Statistical Package for the Social Science (SPSS) software version 22 (IBM Corp, Armonk, NY, USA). A p-value of <0.05 will be used for statistical significance.

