### 2.2 Study design and participants

This is a single centre, 2-arm, 4 weeks randomised, double-blinded parallel trial with equal allocation ratios (1:1). We will follow the Consolidated Standards of Reporting Trials (CONSORT) recommendations for randomized trials (32). Participants will be PLWH (30-60 years) managed under the community-based model (Community Drug Distribution Points-CDDPs) in Wakiso district, central Uganda. The district encircles Kampala, Uganda's capital city with an estimated population of over 2.9 million people. The district has the highest prevalence (10%) of HIV in Uganda. Over 3,801 PLWH are currently receiving the HIV care from CDDPs in Wakiso District (33). The study inclusion and exclusion criteria are presented in Table 2. The study will be announced during the drug refill days and interested patients will be provided with more information about the study before obtaining their consent to participate.

Demographic and medical information will be collected from all consented patients,

[figure not shown]
The study participants will be randomly allocated to consume twice-daily 300 mL of either 10% or 30% pulp of T. indica fruit juice, **figure 1**. Both participants and the study team will be blinded to the intervention materials. Measurements will be performed at three different timelines: 1) Baseline, 2) Week two of the study, and 3) Endline (week four of the study).

Compliance to the study protocol will be confirmed by weekly telephone inquiries, and by counting the returned empty juice bottles or unused study products at each follow-up visit. Participants will be asked to maintain their habitual dietary regimen.

Any reported unusual gastrointestinal side effects, including abdominal pain/cramps, heartburn, stomach acid/reflux, nausea, vomiting, abdominal rumbling, bloating, belching, excess gas/wind, stool type, etc, during the study will be recorded. Patients will be encouraged to contact a study staff by phone or e-mail if they experience any adverse health-related impacts of the interventions. In the case of *T. indica* fruit juice intolerance, patients will be excluded.

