# Randomisation and blinding

A biostatistician of Mildmay hospital will develop computer-generated sequence to randomly allocate participants to each of the two study arms, as shown in figure 1. The biostatistician responsible for generating the allocation sequences will not have any study-related tasks, for example, inclusion or examination of participants. The two juice prototypes will be blinded by assigning a secret code to each of the intervention products. As such, blinding of the investigators and participants will be undertaken to ensure a double-blind intervention. Moreover, the statistical analyses of the main endpoints will be done before breaking the intervention product concealment.

BP, Blood Pressure; BC, Body composition; FBG, Fasting Blood Glucose; TG, Triglycerides; Tc, Total cholesterol; PA, Physical Activity; PWV, Pulse Wave Velocity; WC, waist circumference.

Figure 1: Schematic overview of the study protocol.

Table 2: Eligibility criteria for study participants

Inclusion criteria	Exclusion criteria			
Triglycerides ≥150 mg/dL	Taking dietary supplements			
TLD regimen (ART) for ≥12 months	TB co-infection, renal failure disease, liver cirrhosis, chronic pancreatitis			
95% ART adherence in last 6 months 	Pregnancy and Lactation or regular sport activity			
Virally suppressed (most recent results viral load suppressed within the last 12 months) 	Parallel participation in another clinical trial			
PLWH aged ≥30≤60 years.	On treatment for; dyslipidaemia, hypertension or			
No plans to change location in the next 6 months	diabetes and oral hypoglycaemic drugs			
	Very low blood pressure (< 90/50 mmHg)			
	Not willing to consent or unable to consent			

ART, Antiretroviral Therapy; DBP, Diastolic blood pressure; FGD, Focus group discussion; SBP, systolic blood pressure; TLD, Tenofovir Lamivudine Dolutegravir; WC, waist circumference.

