# 2.3.1 Study outcomes

The primary endpoint will be changes in Triglycerides (TG). Secondary outcomes will include changes in fasting blood glucose and plasma levels of lipids, and parameters of vascular function, **Table 3**.

Table 3: Study outcome measures

Primary outcome measures	Secondary outcome measures	Exploratory outcomes	
Triglycerides [mg/dL]	PWV [m/s], Blood pressure [mmHg]	BMI [kg/m²]	
	Facting Pland always [mg/dI]	Fat mass composition	
	Fasting Blood glucose [mg/dL]	Waist circumference [cm]	
	HDL-c, LDL-c, Total cholesterol [mg/dL]		
	AIx (%), MAP		

BMI, Body Mass Index; PWV, Pulse Wave Velocity; HDL-c, High Density Lipoproteins; LDL-c, Low Density Lipoproteins; AIx, Augmentation Index; MAP, Mean Arterial Pressure

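### The main comparison is not stated to adjust for the baseline value the trial already collects, so precision is given up at no saving

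*Combined protocol and SAP*

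**What the plan says.** The whole analysis plan is one paragraph, section 6 of the combined protocol and SAP. For the arm comparison it states: "Student t-test will be applied to compare means of endpoints between patient groups". It then adds: "To account for any missing data, analyses will be conducted using linear mixed models". No covariate is listed for the t-test, and no fixed effects, baseline term, covariance structure or visit contrast for the mixed model.

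Section 2.3.1 defines the primary outcome: "The primary endpoint will be changes in Triglycerides (TG". Section 2.2 sets the measurement times as "1) Baseline, 2) Week two of the study, and 3) Endline (week four of the study", so a baseline value is collected. Table 2 requires TG of at least 150 mg/dL for entry. The documents do not say whether that eligibility reading also serves as the baseline.

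On scale, section 6 says "Outcome variables will be checked for normality and transformed where necessary", without a rule. On significance it says "A p-value of <0.05 will be used for statistical significance". It states that there is no power calculation and gives no sample size. No other section adds a baseline term.

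**The concern.** Defining the endpoint as a change brings baseline in by subtraction, which amounts to fixing its slope at 1. Covariate adjustment estimates the slope from the data. When baseline and follow-up are imperfectly correlated, the best slope is below 1, and subtraction carries extra baseline noise into the comparison. Randomisation keeps both estimates unbiased, so what is at stake is the width of the confidence interval. That matters in a proof-of-concept trial with a pragmatic, unstated sample size, because the better method uses only data that will be collected anyway.

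**Working it through.** The plan has no figure to reproduce: it states no sample size, SD, effect size or correlation. The question is how much variance baseline adjustment removes.

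**Inputs.** From the documents: two arms at 1:1; visits at baseline, week 2 and week 4; TG entry threshold of 150 mg/dL. Assumed: log TG normal with equal variance at each reading; correlation ρ between any two readings of 0.5-0.8 before selection; the threshold lies at the top 26.4% of the distribution. That percentage is the hypertriglyceridemia prevalence in the earlier Ugandan study cited in section 1.1. It is not a figure for this trial, which also excludes people treated for dyslipidaemia.

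**Step 1: outcomes not restricted by eligibility.** With unit variance, the per-participant variance is 2(1−ρ) for the change score and 1−ρ² for the adjusted comparison. The ratio is (1+ρ)/2, which is 0.80 at ρ = 0.6 and 0.90 at ρ = 0.8: a saving of 20% and 10%.

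**Step 2: effect of the TG threshold.** For the top 26.4%, z = 0.631 and λ = φ(z)/0.264 = 1.238. The variance of the selected reading is V = 1 + zλ − λ² = 1 + 0.781 − 1.533 = 0.248. Step 1 therefore cannot be used for TG as it stands.

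**Step 3: eligibility reading is also the baseline.** The adjusted variance is 1−ρ²; the change-score variance is (1−ρ)²V + (1−ρ²). The ratio is (1+ρ)/[(1+ρ) + (1−ρ)V].
- ρ = 0.5: 1.5/(1.5 + 0.124) = 0.924
- ρ = 0.8: 1.8/(1.8 + 0.050) = 0.973

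**Step 4: baseline is a separate reading.** Let k = ρ²(1−V). The correlation left after selection is r = (ρ−k)/(1−k), and the ratio is (1+r)/2.
- ρ = 0.5: k = 0.188, r = 0.312/0.812 = 0.384, ratio 0.692
- ρ = 0.8: k = 0.481, r = 0.319/0.519 = 0.615, ratio 0.807

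Simulation with 3 million draws agrees with steps 3 and 4 to within 0.001.

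| Adjusted / change-score variance | ρ = 0.5 | 0.6 | 0.7 | 0.8 |
|---|---|---|---|---|
| TG, same reading | 0.924 | 0.942 | 0.958 | 0.973 |
| TG, separate reading | 0.692 | 0.726 | 0.763 | 0.807 |

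Moving the cut-off to the top 15% or top 40% gives about 0.91-0.98 (same reading) and 0.69-0.82 (separate reading), so the result does not hinge on 26.4%.

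**Step 5: cost of estimating the slope.** With n per arm, the adjusted variance rises by a factor of about (2n−3)/(2n−4). At n = 15 this is 27/26 = 1.038, and 0.973 × 1.038 = 1.010: the gain is gone. At n = 50 it is 97/96 = 1.010, and 0.924 × 1.010 = 0.933. Simulation of 40,000 trials per setting at 15, 25 and 50 per arm gave these ranges (confidence interval width at 25 per arm only):

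| | Variance ratio | CI width ratio |
|---|---|---|
| TG, same reading | 0.934-1.010 | 0.972-0.998 |
| TG, separate reading | 0.699-0.836 | 0.841-0.908 |
| Unrestricted, ρ 0.6-0.8 | 0.810-0.935 | 0.904-0.960 |

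**Step 6: would the planned mixed model already do this?** Only if baseline is entered suitably, which is not stated. With complete data, an unstructured covariance and baseline treated as one of the outcomes, a direct check gave the same week 4 t statistic as the change-score t-test (−0.20297 for both). That form recovers none of the precision.

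**The case against.** The strongest reply is that nothing here is wrong. A change-score comparison is valid in a randomised trial, the plan calls itself a proof of concept, and for the primary outcome the gain may be slight: if the eligibility reading is the baseline, the confidence interval at 25 per arm narrows by at most 2.8%. All of that stands. The larger TG saving needs a separate baseline reading, which the documents do not establish.

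It can also be said that the missing-data sentence already makes the mixed model the operative analysis. That is a fair reading, and so is the reading that the model is used only if data are missing. Under either, no baseline term is stated.

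A reader might go further and infer that two unranked methods, an unstated visit and an open scale inflate the type I error. The documents do not support that. It would need a rule of reporting the smallest p-value, and the plan states none. The section on randomisation and blinding has the main endpoints analysed before the product code is broken, which limits choice by direction. In a "single centre, 2-arm, 4 weeks randomised, double-blinded parallel trial" whose last visit is called the endline, week 4 is the ordinary reading of the contrast. "Figure 1: Schematic overview of the study protocol" was not available in the text reviewed and may show the schedule by outcome. These are missing details worth writing down, not demonstrated errors.

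A reader might also apply the unrestricted formula to TG and expect a saving of 15-35% (from (1+ρ)/2 at ρ of 0.7 down to 0.3). That ignores the entry threshold.

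**Conclusion.** The point holds as a missed improvement in precision. Neither method in section 6 is stated to use baseline as a covariate, although it is measured. The large-sample variance saving for TG is about 3-8% or about 19-31%, depending on which reading is baseline, and can be nil at about 15 per arm in the first case. For outcomes not restricted by eligibility it is about 10-20% at correlations of 0.6-0.8. Every one of these figures rests on assumed correlations and normality; the TG figures also rest on the assumed cut-off. No bias, invalidity or type I error inflation is claimed. Confidence is medium: the gap in the text is plain, but the gain for the primary outcome is uncertain.

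**What to change.** Replace the t-test as the main comparison with the arm difference in TG at week 4 from a linear mixed model of the week 2 and week 4 values. Include arm, visit, arm-by-visit, baseline TG and baseline-by-visit, and take all randomised participants in their assigned arm. Use the same baseline-adjusted model for the other outcomes, with ANCOVA for any measured only at week 4 after baseline, and keep the t-tests as supportive.

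While editing, make three clarifications: name this as the primary analysis, with its covariance structure; fix the TG scale in advance (log TG, reported as a ratio of geometric means with a 95% confidence interval, is one sound choice); and say whether baseline TG is the eligibility reading or a separate one.

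The cost is SAP wording, settled before outcome data are analysed. The planned visits, measurements and SPSS suffice. The only statistical price is a small loss of degrees of freedom, negligible except in a very small trial, where it can cancel a small gain.

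### Both arms drink the juice, so the only stated test is a dose contrast (H2) that cannot by itself establish H1, and the deciding triglyceride test and visit are not named

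*Combined protocol and SAP*

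**What the plan says.** - **Hypotheses (section 1.2).** H1 predicts that drinking the juice improves cardiometabolic response overall, across vascular function, blood pressure, glycaemia and lipids. H2 predicts a dose-response difference.
- **Arms (section 2.2).** Participants are "randomly allocated to consume twice-daily 300 mL of either 10% or 30% pulp of T. indica fruit juice". No juice-free arm is described.
- **Visits (section 2.2).** "Measurements will be performed at three different timelines: 1) Baseline, 2) Week two of the study, and 3) Endline (week four of the study".
- **Outcomes (section 2.3.1).** "The primary endpoint will be changes in Triglycerides (TG", with no visit attached. "Secondary outcomes will include changes in fasting blood glucose and plasma levels of lipids, and parameters of vascular function". Table 3 ranks the outcomes as primary, secondary and exploratory.
- **Analysis (section 6).** The first method named is a simple two-group test: "Student t-test will be applied to compare means of endpoints between patient groups". The choice of scale is left until the data are in hand: "Outcome variables will be checked for normality and transformed where necessary". A second method is then named, and it is not ranked against the first: "To account for any missing data, analyses will be conducted using linear mixed models". The threshold closes the section: "A p-value of <0.05 will be used for statistical significance". The threshold is not tied to an outcome, hypothesis or visit, and sidedness is not stated.
- **Entry and blinding (Table 2; Randomisation and blinding).** Entry requires TG of at least 150 mg/dL. The main endpoints are analysed before the product code is broken.

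**The concern.** H1 is a claim about the juice as such, but the plan contains no comparison of juice with no juice. A significant 30% versus 10% difference could be written up as showing that the juice improves cardiometabolic health, and a null result as showing that it does not. Neither conclusion follows from a dose contrast.

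Separately, TG is the sole primary endpoint but its test is not pinned down. There are two post-baseline visits and two candidate analyses, and nothing ranks them. A reader of the final report could not tell from the plan whether the TG result presented is the one that was meant to decide.

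**Working it through.** The plan gives no sample size, power, effect size or SD, so there is no design figure to reproduce. The only number to work from is the 0.05 level, taken here as two-sided.

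**1. What the between-group test compares.** Daily volume is 2 × 300 mL = 600 mL, or 6 × 100 mL. Total polyphenols per 100 mL come from Table 1.
- 10% pulp: 8.30 × 6 = 49.8 mg/day
- 30% pulp: 26.36 × 6 = 158.2 mg/day
- Difference: 18.06 × 6 = 108.4 mg/day

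The test therefore asks whether about 108 mg/day more polyphenols changes the outcome.

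**2. What each result would mean.**
- *Difference found:* if the juice did nothing at any dose, the arms would not differ. Rejecting equality is therefore evidence that dose matters for that outcome. It does not show improvement over no juice, nor improvement across four domains.
- *No difference found:* both doses might work equally well, or neither might work. H1 is not refuted.

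**3. Whether a within-arm fall could stand in for H1.** It could not. Patients are selected on TG of at least 150 mg/dL, so some fall is possible through regression to the mean alone. The problem is greater if the qualifying value also serves as baseline; a separate baseline measurement would remove most of it. The documents give no TG SD or between-visit correlation, so I put no size on it.

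**4. TG error if either visit could decide.** Let Z₂ and Z₄ be the test statistics for TG change at weeks 2 and 4, standard bivariate normal with correlation ρ under no effect. The error is 1 − P(|Z₂| < 1.96 and |Z₄| < 1.96). The value of ρ is assumed.

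| ρ between change scores | Type I error |
|---|---|
| 0 | 1 − 0.95² = 0.0975 |
| 0.5 | 0.0907 |
| 0.8 | 0.0781 |
| 0.95 | 0.0646 |

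With the visit and model fixed in advance, it is 0.05.

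**5. Conditional illustration for the wider outcome list.** Counting systolic and diastolic pressure separately, TG and the nine secondary measures make ten: TG, HDL-c, LDL-c, total cholesterol, glucose, systolic pressure, diastolic pressure, PWV, AIx and MAP. If any one of them at p < 0.05 at one visit were taken as success, with no true effect:
- Equal correlation of 0.3, 0.5 or 0.7 among all ten: 0.351, 0.287, 0.213.
- Correlation in blocks (four lipids; glucose; systolic, diastolic and MAP; PWV and AIx), within/between-block correlation 0.3/0, 0.5/0.1, 0.5/0.3, 0.7/0.2, 0.7/0.5: 0.387, 0.358, 0.332, 0.316, 0.265 (simulation, 400,000 runs each).

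The range is about 21% to 39%. MAP is a separate variable here because section 2.4.2.1 derives it from Arteriograph readings taken supine on the right arm, while section 2.4.2.2 takes blood pressure with a Seca monitor, seated, on the left arm. MAP is therefore not fixed by the recorded systolic and diastolic values.

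**The case against.** The strongest reply is that the plan already has its hierarchy: one primary endpoint, a ranked outcome table and analysis under code. In a proof-of-concept trial with no power calculation, unadjusted secondary tests are common. This largely stands. A reader might infer from the single threshold that any significant outcome counts as success, with a false-positive chance of 21% to 39%. No section states such a rule. H1's wording is closer to requiring all domains than any one. If one outcome per domain all had to reach two-sided 0.05, the error under no effect would be about 0.02% to 0.6% for correlations of 0.3 to 0.7. The multiplicity figure is an illustration of what loose reporting could do, and not a property of the plan.

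A reader might also infer that a dose difference says nothing about H1. That is too strong, because such a difference argues against the juice being inert at both doses for that outcome. Nor is a within-arm analysis planned; regression to the mean matters only if one were brought in to support H1. Figure 1 could not be read for this review and may show a separate baseline.

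The open choice of scale is a lesser matter, since the stated trigger is a normality check and not the p-value.

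Two things survive. Naming TG as primary does not turn a dose contrast into a test of H1. Analysis under code limits choice by direction, but p-values by visit and method remain visible, and coding does not say which of them decides.

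**Conclusion.** The point holds on two counts. First, the design and the stated comparison address H2 only; this rests on the text and needs no assumption. Second, the primary TG analysis is not uniquely defined, because two methods are unranked and no deciding visit is named. Week 4 is the natural reading of Endline, but it is not stated to be the deciding visit. The cost in error is modest: about 6.5% to 9.75% in place of 5%, and only if a result at either visit were accepted, under assumed correlations.

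The randomised comparison itself remains valid. What is unprotected is its interpretation, so this should be corrected before analysis.

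**What to change.** Amend sections 1.2, 2.3.1 and 6 as follows.

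1. Make the single primary test, at two-sided 0.05, the 30% versus 10% difference in TG at week 4 from one pre-specified linear mixed model. A suitable form is log TG as response, visit and arm-by-visit terms, a common baseline mean (or baseline adjustment), unstructured covariance, and results back-transformed.
2. Label the Student t-test, which makes no baseline adjustment, a sensitivity analysis.
3. State that the primary result addresses H2 for TG. H2 as worded also spans more than TG, so the limit needs saying.
4. Reword H1 to match the design, or report it descriptively, and state that a within-arm change does not establish it.
5. Report week-2 TG and the secondary and exploratory outcomes as non-confirmatory estimates with 95% confidence intervals.

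This uses data already planned and needs no extra participants, visits or assays. The downside is that nominally significant secondary results, and H1 itself, cannot be presented as confirmed.

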### 7. Ethics and regulatory approvals

All study procedures will be conducted in accordance with the Helsinki Declaration and the study protocol will be registered in a public database (ClinicalTrials.gov). Research approval and permit has been sought and granted by the research ethics committee of Clarke International University and Uganda National Council of Science and Technology. All willing participants will be asked to voluntarily sign an informed consent form at the point of recruitment. The research team will protect the data from disclosure outside the research according to the terms of the research protocol and the informed consent document. The investigator will treat all information and data of participants as confidential and shall not disclose such information to any third parties or use such information for any purpose other than the performance of the study. The subject's name or other identifiers will be stored separately from their research data and replaced with a unique code to create a new identity for the participant. It is anticipated that the results of the study will be presented at national and international conference or published in an international peer reviewed journal. Authorship to publications will be determined in accordance with the requirements published by the International Committee of Medical Journal Editors and in accordance with the requirements of the respective medical journal. Each participant will be offered a healthy snack and also compensated USD 8 each visit to cater for transport.

